#### 4.47 **BLINDING**

Blinding is not possible in this one arms study

#### 4.48 OVERVIEW OF STUDY CONDUCT

The Table 1 provides an overview of the assessment requirements for the study. All testing and assessments should be conducted at the study site.

				Foll	ow_Un Vi	cite
	Baseline	Procedure	Pre- Discharge	30-Day	6-Month	1-Year
	Within 45 days prior to enrollment		Prior to discharge (or within 5 days after index procedure)	30-45 days after index procedure	150-210 days after index procedure	320-410 days after index procedure
Informed Consent	Х					
Medical History and Physical Exam	Х			Х	Х	Х
Medication Use	Х			Х	Х	Х
Creatinine (non-standardized)	Х		X^			Х
Hemoglobin A1C		Χ †				Х
Rutherford Clinical Category Assessment	Х			X	Х	Х
Walking Impairment Questionnaire (WIQ)	Х			X	Х	Х
Ankle Brachial Index (ABI)	Х			Х	Х	Х
Angiogram		Х				
Duplex Ultrasound			X	*	Х	Х
Adverse Event Evaluation		Х	X	Х	Х	Х

**Table 1: Study Assessment Requirements** 

† Blood draw for hemoglobin A1C assessment can occur at the baseline evaluation or during the procedure.

\* The first duplex ultrasound can occur any time within 45 days of the index procedure.

^ Cr at 72 hours post procedure +/- 24 hours

#### 4.49 REQUIRED ASSESSMENTS AND TESTS

The following section details the study-required assessments and tests.

#### 4.50 MEDICAL HISTORY AND PHYSICAL EXAMINATION

The subject's clinical history and pre-existing conditions will be assessed and documented at baseline and at every visit at 30 days, 6 months and 1 year.

#### 4.51 MEDICATION USE

The subject's medication use will be documented at baseline, at 30 days, 6 months and 1 year. Medication use will include anticoagulants and antiplatelet medications.

#### 4.52 CREATININE

Creatinine (non-standarized) will be obtained and documented at baseline, 72 hours post procedure (+/- 24 hours) and at 1-year follow-up visit.

### 4.53 HEMOGLOBIN A1C (HB A1C)

Glycosylated hemoglobin (Hb A1C) will be obtained and documented at either baseline or on the day of the procedure, and at the 1-year follow-up visit.

### 4.54 RUTHERFORD CLINICAL CATEGORY ASSESSMENT

The subject's clinical status as indicated by RCC per clinical description will be assessed and documented at baseline and all follow-up visits.

### 4.55 ANKLE-BRACHIAL INDEX (ABI)

The subject's ABI will be measured and documented at baseline and all follow-up visits. An ABI is the ratio of the highest ankle systolic pressure to the highest brachial systolic pressure.

#### 4.56 WALKING IMPAIRMENT QUESTIONNAIRE (WIQ)

Each subject will undergo a WIQ assessment and the results will be documented at baseline and all follow-up visits. The WIQ is an interviewer-administered subject-reported functional assessment focused on difficulty in walking.

#### 4.57 ANGIOGRAM

For procedural angiogram requirements see Section 4.62. Angiograms will be obtained per the Angiographic Protocol determined by the Angiographic Core.

### 4.58 **DUPLEX ULTRASOUND (DUS)**

It is required that the subject undergo a DUS, the results be documented and copies of the scan be sent to the core laboratory. DUS is required within 45 days of the index procedure (at either the pre-discharge or 30-day visit), at 6 months, and at 1 year post-procedure. DUS will be obtained as per Core lab protocol.

### 4.59 ADVERSE EVENT (AE) EVALUATION

Adverse event evaluations will be performed during the procedure, prior to discharge, and at all follow-up visits. Refer to Section 4.20 and 4.3 and Definition section for AE definitions.

#### 4.60 **BASELINE REQUIREMENTS**

Informed consent must be obtained from each subject prior to enrollment into the study in accordance with the ICH/GCP guidelines, Declaration of Helsinki, and pertinent individual country laws/regulations.

Table 2 summarizes the list of all assessments and tests that are required at baseline. The blood sample for the assessment of creatinine will be taken at baseline. The blood sample for the hemoglobin A1C test may be taken at baseline or during the procedure.

### **Table 2: Baseline Requirements**

	Baseline Requirements	Timeframe Window
--	-----------------------	-------------------------

Informed consent	
Medical history and physical exam	
Creatinine	
Hemoglobin A1C †	Within 45 days prior to enrollment
Concomitant medication use	
Rutherford Clinical Category assessment	
Walking Impairment Questionnaire (WIQ)	
Ankle Brachial Index (ABI)	

† Blood draw for hemoglobin A1C assessment can occur at the baseline evaluation or during the procedure.

#### 4.61 **PROCEDURE REQUIREMENTS**

The subject will undergo percutaneous revascularization of the superficial femoral and/or popliteal arteries. The JS + adjunctive PTA will be used to treat all lesion. Operators should have at least a minimum experience with 10 Jetstream cases as a primary operator to qualify to enroll patients in this study.

The following describes the required assessments and activities during the procedure.

#### 4.62 ANGIOGRAM

A sheath will be inserted and after insertion the subject should receive anticoagulation medications as indicated by the Investigator to maintain appropriate clotting time. Selective angiography of the limb to be treated including the distal aorta, bilateral iliac, ipsilateral femoral, popliteal and tibial-peroneal vessels (to the pedal level) will be performed to identify the anatomical characteristics of the vasculature and to best isolate and define the lesion. If a pre-procedure assessment has been completed with CTA/MRA, the angiography can be limited to the target vessel, with a baseline assessment of run-off. Angiography must be conducted according the Angiographic Protocol (refer to Core Lab requirement). Gadolinium and CO2 are not allowed for use as contract material.

During angiography the Investigator performing the procedure will assess the subject for the angiographic inclusion and exclusion criteria. It is required that a radiopaque ruler be used to define lesion length and define anatomical measurement references. If the subject meets all the angiographic inclusion criteria and does not meet any of the angiographic exclusion criteria, the subject is enrolled when an exchangeable guidewire crosses the target lesion. Upon enrollment, subjects will be then treated with the JS + PTA as per protocol.

Angiographic films, including run-off, will be obtained immediately prior to and after treatment (after JS alone, and after adjunctive PTA or bail out stenting) according to the Angiographic Core Lab Protocol. Capture images that demonstrate the stenosis in two views that minimize the degree of vessel overlap and demonstrate the stenosis in its most severe view. Angiographic results must be sent to the Angiographic Core Laboratory.

The Angiographic Core Laboratory assessments will supersede the measurements by the Investigator performing the procedure for data analysis purposes; however, the measurements by the Investigator performing the procedure will be used to determine subject eligibility at the time of enrollment.

The Angiographic core laboratory will also assess stent fracture location and severity at baseline prior to any treatment and post atherectomy to assess for additional/worsening fractures.

### 4.63 TREATMENT OF THE TARGET VESSEL

### 4.641 TARGET LESION

The lesion intended for treatment at the time of the index procedure that meets the inclusion criteria and none of the exclusion criteria will be considered the "target lesion." Each subject can have only one target lesion. The point of enrollment is defined as the moment an exchangeable guidewire and treatment catheter cross the target lesion in the true lumen.

If there are 5 cm or less between diseased segments needing treatment in the SFA and/or popliteal artery, then it can be considered one lesion (see example below). If there are more than 5 cm between diseased segments, they will be considered separate lesions and count as two or more lesions. If multiple lesions in the target vessel require treatment, patient not eligible for enrolment

### 4.642 TREATMENT OF NON-TARGET VESSELS

Lesions in the ipsilateral or contralateral iliac arteries or ipsilateral common femoral arteries to the target limb that require treatment may be revascularized during the index procedure. These lesions must be successfully treated prior to the point of enrollment. Stent placement in the common femoral arteries will exclude patient from enrolment.

If a patient has an infrapopliteal lesion that requires treatment for significant (> 70% stenosis or occlusion) stenosis, patient cannot be enrolled.

Lesions in the non-target limb may be treated during the index procedure, but not within or equal 30 days following the index procedure.

### 4.643 JS + PTA GROUP PROCEDURES

The selection of the JS XC device will be at the discretion of the treating physician. In general however, the 2.4 XC is for vessel diameter > 5 cm and 2.1 XC for 4-5 cm. The plaque excision procedure will follow the steps described in the published manual by [name] et al. The Spartacore (Abbott) or JetStream Wire (Boston Scientific) are recommended with the use of the JetStream device. The Grand Slam wire and hydrophilic wires are not recommended. Filters are highly encouraged but left to investigator's discretion. If a filter is used, the off label use of the Nav-6 (Abbott) filter is

recommended. The long BareWire will need to be used. JetStream IFU has no recommendations on filter use.

Residual stenosis following the plaque excision treatment must be documented by angiography per the Angiographic Protocol. It is recommended that residual stenosis be < 50% prior to treatment with adjunctive PTA.

Dilation of the lesion following JS has to be done with a 1:1 balloon size and avoidance of oversizing. The diameter of the study balloon will be selected based on the vessel reference diameter distal to the target lesion. Balloon inflation should be limited to within the stent. See section 4.43 for details.

If there is a complication during JS, treatment is at the operator's discretion. If a perforation occurs in the area of plaque excision, it must be sealed and distal outflow must be established.

#### 4.644 ADJUNCTIVE PROCEDURES

Adjunctive procedures besides PTA should be avoided if possible. In the event of a major flow limiting dissection (type D and higher), perforation, or occlusive complication (e.g., recoil), prolonged balloon inflation (5 minutes) must be attempted first. All efforts should be made to eliminate the need for bail-out stent placement. In cases where the results after prolonged balloon inflation are suboptimal, bail-out stenting is allowed. A cine following the prolonged balloon inflation must be captured; all bail-out stenting procedures will be reviewed by the Angiographic Core Laboratory. Adjunctive treatment with cutting balloons or scoring balloons is not allowed. Adjunctive or primary PTA should be done with a non-compliant or semi compliant balloon sized 1:1 to vessel size. Adjunctive stenting is performed only with self-expanding nitinol stent. Drug coated stents, covered stents, or drug coated balloons are not allowed in the study.

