#### 4.43 STUDY TREATMENT RULES

- 1. No other debulking devices, cutting/scoring balloons or cryogenic balloons may be used in before or after the Jetstream XC
- 2. Balloon inflation is per operator's discretion but should not exceed burst pressure and should be at least at nominal pressure. Operators should increase balloon pressure beyond nominal pressure only if balloon full expansion does not occur at nominal pressure. If higher balloon pressure beyond nominal is felt necessary, then pressure is increased at 1 atm every 5 seconds until full balloon expansion occurs.
- 3. Semi-compliant balloons are recommended
- 4. The only adjunctive therapies allowed are PTA and bailout stenting:
  - Bailout stenting is allowed if > 30% residual stenosis remains or for perforation
  - Type D dissection leading to flow limitations
  - Self-expanding nitinol stents are recommended if needed
  - Covered stents are allowed only if there is a perforation
  - Bailout stenting is not allowed if the lesion has ≤ 30% residual stenosis
  - Only one leg may be treated per patient. Patient is enrolled only once in the study.
  - Drug coated stents or Drug coated balloons are not allowed.

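### Section 4.43 permits a covered stent for a perforation and section 4.644 forbids it, so the same act is protocol treatment under one section and a deviation under the other

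*Combined protocol and SAP*

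**What the plan says.** Three sections of the protocol bear on stenting after a perforation.

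- **Section 4.43 (study treatment rules).** Perforation is an indication for bail-out stenting: "Bailout stenting is allowed if > 30% residual stenosis remains or for perforation". The stent type is advisory: "Self-expanding nitinol stents are recommended if needed". Covered stents have one permitted use: "Covered stents are allowed only if there is a perforation".
- **Section 4.643 (JS + PTA group procedures).** "If there is a complication during JS, treatment is at the operator's discretion". The next sentence reads: "If a perforation occurs in the area of plaque excision, it must be sealed and distal outflow must be established". The means of sealing is not named.
- **Section 4.644 (adjunctive procedures).** Perforation is one of the events that the section governs, and balloon inflation has to come first: "In the event of a major flow limiting dissection (type D and higher), perforation, or occlusive complication (e.g., recoil), prolonged balloon inflation (5 minutes) must" come before anything else. If the result is still inadequate, bail-out stenting is permitted. The section then fixes the stent type, "Adjunctive stenting is performed only with self-expanding nitinol stent", and closes with: "Drug coated stents, covered stents, or drug coated balloons are not allowed in the study".

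The primary effectiveness endpoint (section 4.2) counts bail-out stenting of the index lesion during the procedure as a TLR. The primary safety endpoint, 30-day MAE, includes bail-out stenting through its TLR component.

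**The concern.** An operator who relies on section 4.43 to place a covered stent for a perforation breaches section 4.644. The complication is foreseeable: section 6.3 lists arterial perforation and rupture among the device risks, section 4.658 makes perforation an individual in-hospital and 30-day MAE component, and section 1.0 describes use in in-stent restenosis as off label and investigational. An operator should not have to settle a conflict between two sections in the middle of a procedure.

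Records are also at stake. Section 12 defines a deviation as any departure from the protocol, and section 4.655 requires deviations to be reported to the sponsor. Whether a covered stent placed for a perforation is reportable depends on which section the site or monitor reads, so two sites could record identical events differently. Deviation counts carry weight here: section 8 lets unresolved non-compliance lead to a site's probation or withdrawal, and section 11.0 ties authorship partly to protocol deviations.

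**Working it through.** No figure in the plan rests on this point, so the check is a comparison of texts.

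**Step 1. Set the rules side by side.**

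| Question | Section 4.43 | Section 4.643 | Section 4.644 |
|---|---|---|---|
| Does it cover perforation? | Yes, by name | Yes, by name | Yes, by name |
| Covered stent for perforation? | Allowed | Not addressed | Not allowed, no exception stated |
| Self-expanding nitinol stent? | Recommended | Not addressed | The only type permitted |
| Operator discretion? | Not stated for stent type | Yes, for complications during atherectomy | Not stated for stent type |

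The sections disagree on covered stents and on whether the nitinol stent type is advisory or mandatory.

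**Step 2. Can both be followed?** Not if a covered stent is placed for a perforation. Section 4.644 is not silent on perforation in a way that would let section 4.43 supply the exception: it names perforation, permits stenting for it after balloon inflation, and then bars covered stents throughout the study. Section 12 also includes perforations in its definition of adjunctive treatment.

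**Step 3. Does other text settle it?**

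- Section 4.643 gives discretion for complications during atherectomy. That does not clearly reach a perforation at the later balloon step, and nothing says that it overrides section 4.644.
- The covered-stent wording in section 4.4 and in exclusion criterion 21 of section 4.4.2 concerns earlier treatment of the target lesion, not bail-out.
- The changes listed at the end of the document concern exclusion criteria, blinding, hemoglobin A1C, creatinine and duplex ultrasound. None touches sections 4.43, 4.643 or 4.644.

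**Step 4. Trace the effect on the primary endpoints.**

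| Event | Primary effectiveness (6-month TLR) | Primary safety (30-day MAE) |
|---|---|---|
| Perforation sealed without a stent | Not counted by itself | Not counted by itself |
| Perforation, bare nitinol bail-out stent in the index lesion | Counted | Counted |
| Perforation, covered bail-out stent in the index lesion | Counted | Counted |

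The second and third rows are identical because the endpoint definitions make no distinction by stent type. Only a move between the first row and the other two would change a count.

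**Step 5. Bound the number of patients.** The documents give no perforation rate for this device in in-stent restenosis. As an assumption, take 1% to 3% of the planned maximum of 140 patients: 140 × 0.01 = 1.4 and 140 × 0.03 = 4.2. This is an upper bound on the patients for whom the conflict matters, because section 4.644 requires prolonged balloon inflation first and only perforations not controlled by it reach the choice of stent.

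**The case against.** The strongest reply is that an operator already has room to act. Section 4.643 leaves complications during atherectomy to the operator, and sections 4.655 and 9.8 provide for emergency deviations to protect a patient's life or physical well-being, with reporting. Section 4.43 can also be read as a specific exception to a general bar in section 4.644. On that view, what remains is an editorial matter and some deviation reporting.

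Part of this stands: the discretion and emergency provisions soften the practical risk. They do not resolve the conflict. The discretion is tied to the atherectomy step. The emergency route treats the act as a deviation, which section 4.43 says it is not. The reading as an exception is possible, but section 4.644 deals with perforation itself and states no exception.

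The objection is right about the analysis. A reader might infer three stronger points, and the documents support none of them.

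- *That the emergency is itself a primary endpoint event.* Perforation appears only among the individual in-hospital and 30-day MAE components.
- *That the choice between a covered and a bare stent moves the primary endpoints.* Bail-out stenting of the index lesion counts either way.
- *That the conflict affects the analysis by actual treatment in section 5.23.* That section defines no category by stent type. If the analysis is underspecified, that is a separate matter.

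**Conclusion.** The contradiction is real and current. Sections 4.43 and 4.644 give opposite rules on covered stents for a perforation and differ on whether self-expanding nitinol stents are mandatory; section 4.643 does not say which prevails. The consequences are unclear instructions for a foreseeable complication and inconsistent deviation status for the same act. It should be corrected for patient safety and consistent conduct.

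No effect on either primary analysis is shown. One would arise only if the conflict changed whether a stent is placed in the index lesion, and the documents give no basis for estimating how often that would happen. The 1.4 to 4.2 patients rest on an assumed 1% to 3% perforation rate and are a ceiling on patients facing the question, not a count of endpoint events caused by the conflict.

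This review takes no view on which rule is clinically right.

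**What to change.** The sponsor's clinicians should reconcile sections 4.43, 4.643 and 4.644 into one statement, placed in one section and cross-referenced from the other two. It should settle whether and when a covered stent may be used, whether the stated stent type is required or recommended, and how the discretion in section 4.643 relates to both. Sites should then be notified, so that deviations are recorded on one basis.

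The endpoint definitions should stay as they are, with bail-out stenting of the index lesion as the counted event. A further sentence saying that any stent placed under the reconciled rule counts would be redundant for the index lesion. For a stent placed elsewhere, it would widen the primary endpoints.

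The cost is about one sentence in a protocol amendment, which section 9.7 sends to the IRB, and a letter to sites. The sample size and the planned analyses do not change.

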#### 4.645 PROCEDURE COMPLETION

An angiogram of the treated segment(s) must be recorded for subsequent Angiographic Core Laboratory analysis of the post-treatment residual stenosis.

The end of the procedure is defined as the time after a complete angiogram, including runoff, has been performed **AND** the last guidewire and catheter have been removed. If the subject returns to the procedure room and a guiding catheter is reinserted and dilation is performed, this is considered a re-intervention and should be documented accordingly. The sheath(s) may be removed at the physician's discretion.

#### 4.646 ADVERSE EVENT EVALUATION

An AE evaluation will be performed during and at the end of the procedure. See Section 4.20 for the AE definitions. Adverse event evaluations will also occur prior to discharge and at all follow-up visits.

#### 4.647 MEDICAL ANTICOAGULANT/ANTIPLATELET THERAPY

### Pre-Procedure

The subject should be optimally medically-managed for peripheral arterial disease per the standard institutional regimen.

### Peri-Procedure

The subject should receive anticoagulation as indicated by the Investigator to maintain appropriate activated clotting time (ACT). For patients receiving bivalirudin, ACT is not necessary. For patients receiving heparin, the ACT goal is 250 seconds (Using iStat) or 300 seconds using Hemochron. If patient is on clopidogrel or other ADP receptor antagonist, this will be continued as prescribed. If patient is on Ticagrelor, only 81 mg of ASA daily should be prescribed. If patient is not on ADP receptor antagonist, he will be loaded with clopidogrel 600 mg po x one dose (or equivalent drug).

#### **Post-Procedure**

The subject should be optimally medically-managed for peripheral arterial disease per the standard institutional regimen. Post procedure, patients should be continued on clopidogrel (or an equivalent drug) 75 mg po daily for 3 months and aspirin indefinitely. If patient is on ticagrelor, asa 81 mg po daily is prescribed.

#### 4.648 FOLLOW-UP REQUIREMENTS

All subjects are required to complete all follow-up visits as shown in Figure 2.

Figure 2: Study Diagram of Follow-up Requirements

#### 4.649 PRE-DISCHARGE FOLLOW-UP REQUIREMENTS

All subjects are required to have a pre-discharge assessment. Pre-discharge assessment requirements are listed in Table 3.

Pre-Discharge Requirements	Timeframe
Adverse event evaluation	Prior to discharge (or within 5 days
Duplex Ultrasound*	after index procedure)

#### **Table 3: Pre-Discharge Assessment Requirements**

\* First duplex ultrasound can occur any time within 45 days of the procedure. Must be conducted per Duplex Ultrasound Protocol. Copies must be sent to the Duplex Ultrasound Core Laboratory for review.

